Study Protocol and Statistical Analysis Plan

for

FitMi Plus: Smart Functional Modules for Practicing Activities of Daily Living after Stroke

ClinicalTrials.gov Identifier: NCT03935425

Date: 12/31/2023

Background

Stroke is the leading cause of chronic disability in the United States, with over 700,000 people experiencing a new stroke each year. Other conditions that lead to chronic disability are spinal cord injury, hand and wrist trauma, multiple sclerosis, traumatic brain injury, muscular dystrophies, back injury, and cerebral palsy. In all these conditions the human motor system retains substantial capacity for plasticity, and thus intensive rehabilitation exercise can reduce long-term movement impairment. Unfortunately, access to intensive rehabilitation is limited due to cost and therapists' time constraints, preventing many individuals from receiving the amount of therapy required to maximize their potential recovery. There has been a recent surge in the development of technologies, services, and methodologies for enabling individuals to practice on their own at home. However, existing technologies for home therapy have not been widely adopted in actual practice. The most common approach to home-based therapy is simply providing patients with printed sheets of exercises. This approach is not motivating, does little to incorporate current theories on effective rehabilitation, and is associated with low compliance and high dropout rates.

Flint Rehab's existing FitMi system has demonstrated success in motivating individuals with stroke to perform moderately intense therapy with relevant feedback, individually tailored exercises, and an appropriate challenge level. However, FitMi does not encourage the functional practice of activities of daily living. Recognizing this, we developed an expanded version of FitMi called FitMi Plus that combines objects commonly used during activities of daily living into distinct Functional Modules, allowing users to practice specific functional tasks while engaging with a motivating software platform.

Trial Design

This study was a double-site, single-blind randomized controlled trial evaluating the efficacy of homebased functional training with FitMi Plus compared to non-functional exercise (FitMi Basic) with individuals with chronic stroke (N=50). This randomized controlled trial was carried out at two separate study sites: the University of California, Irvine, and Rancho Los Amigos National Rehabilitation Center in Downey, CA, with the specific objective of enrolling 25 participants at each study site by the end of the project period. Participants were invited for an initial assessment to confirm they met the inclusion criteria and to establish baseline measures. Participants provided informed written consent. Qualifying participants were randomly assigned to either the FitMi Plus group or non-functional exercise (FitMi Basic) group. Participants in both groups were instructed to perform self-guided therapy for at least 3 hours/week for three consecutive weeks. Appropriate exercise movements for each participant were selected in collaboration with each participant by a trained therapist.

After the three-week exercise period, participants returned for a post-therapy assessment. At this assessment, participants returned their devices. Participants also returned one month later for a one-month follow-up assessment. The trial was pre-registered on ClinicalTrials.gov (NCT03935425) and approved by the Rancho Research Institute, Inc. Institutional Review Board at Rancho Los Amigos National Rehabilitation Center and University of California, Irvine Institutional Review Board.

Participants

Inclusion criteria included experiencing one or more strokes >6 months prior, Upper Extremity Fugl-Meyer (FM) Score >=15 and <=55 out of 66, absence of moderate to severe upper extremity pain (<= 4 on the 10 point visual-analog pain scale), ability to understand the instructions to operate FitMi, and age <= 85 (as older age could be a confounding variable). Exclusion criteria included having other concurrent severe medical problems, visual deficits, severe neglect or apraxia, or enrollment in other therapy studies. After obtaining consent, participants received a 30-minute training session on how to set up and use their device to perform a prescribed list of exercises. Recruitment aimed to balance the age, ethnicity, and gender of the study participants to be representative of Los Angeles and Orange County in California, USA. All participants provided informed consent.

Using an estimated effect size (Cohen's *d*) of 0.9 based on long-term follow-up data from a previous study (N=18) of functionally oriented home-based exercise with MusicGlove, 22 participants in each group would provide a 90% chance of detecting a significant difference between groups at the 0.05 significance level (one-tailed t-test). To account for 10% dropout, we will recruit 25 participants in each group.

Adaptive randomization was used to ensure matched levels of impairment between the FitMi Plus and FitMi Basic groups. Specifically, subjects were stratified by their UE FM Score into two levels (i.e. 15-35, 36-55) and then randomized by alternating block allocation.

Intervention

Participants randomized to the FitMi Plus group were given a FitMi Plus system with custom 10" touchscreen tablet. Participants randomized to the FitMi Basic group were given a FitMi Basic system with custom 10" touchscreen tablet. For both groups, a supervising rehabilitation therapist selected the exercises for each participant based on their specific impairments and functional goals. All participants received 30 minutes of training from the therapist on how to perform the selected exercises correctly.

Participants in both groups were instructed to perform self-guided therapy for at least 3 hours/week for three consecutive weeks. After the 3-week exercise period, participants returned for an end-of-therapy assessment. At this assessment, participants returned their FitMi Plus or FitMi Basic systems. Participants returned one month later for a follow-up assessment.

Outcomes

The primary outcome measure was the change in Motor Activity Log (MAL) score from baseline to one-month post-therapy to assess increases in self-reported functional use of the upper extremity. MAL was assessed at baseline and one-month follow-up. The secondary outcome measure was the change in Upper Extremity Fugl-Meyer (FM) Score from baseline to one-month post-therapy to assess changes in motor impairment. These measures are widely used in stroke rehabilitation research and have good sensitivity and reliability. All assessments were performed by a blinded, trained evaluator.

Statistical Methods

Statistical analyses were performed using Matlab R2020 software. Change in Motor Activity Log (MAL) from baseline assessment to one-month follow-up was compared between FitMi Plus group and FitMi Basic group using an unpaired two-tailed t-test. We recruited 50 total participants across both study sites. Two participant did not return for long term follow-up and were excluded from final analysis, leading to a final n=48 (13 female, 35 male), with 24 participants in the FitMi Plus group and 24 participants in the FitMi Basic group. Similarly, change in Upper Extremity Fugl-Meyer Score from baseline to one-month post-therapy was compared between groups using an unpaired two-tailed t-test.

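### The stated 90% power belongs to a one-tailed t-test, but the primary analysis is two-tailed; at the planned 22 per group its power is about 83%

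*Combined protocol and SAP*

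**What the plan says.** The sample size is justified under Participants. It starts from an assumed effect: "Using an estimated effect size (Cohen's *d*) of 0.9 based on long-term follow-up data from a previous study (N=18"). It then states the size, the power and the test together: "22 participants in each group would provide a 90% chance of detecting a significant difference between groups at the 0.05 significance level (one-tailed t-test"). Attrition is added next: "To account for 10% dropout, we will recruit 25 participants in each group".

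Under Outcomes the primary endpoint is defined: "The primary outcome measure was the change in Motor Activity Log (MAL) score from baseline to one-month post-therapy". Statistical Methods then says that this change "was compared between FitMi Plus group and FitMi Basic group using an unpaired two-tailed t-test". That section states no significance level. It reports that 50 participants were recruited, that two did not return for long-term follow-up, and that 24 per group were analysed.

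**The concern.** The power statement and the analysis describe different tests of one endpoint. At the same 0.05 level a two-tailed test has a higher critical value in the expected direction than a one-tailed test, so it has less power at the same sample size and effect. The advertised 90% therefore cannot be the power of the test in Statistical Methods.

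Two things are at stake. First, if the trial finds no difference, a reader will judge that result against a 10% chance of having missed the assumed effect, when the real chance is larger. Second, the document leaves two tail conventions attached to the primary outcome. A result that favours FitMi Plus with, for example, a two-tailed p of 0.07 would be significant by the convention used for sizing and not significant by the one used for analysis.

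**Working it through.** **Inputs**

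- Effect size d = 0.9, one-tailed level 0.05, 22 evaluable per group, 10% dropout and 25 recruited per group: Participants, sample-size paragraph.
- Two-tailed unpaired t-test, 24 analysed per group: Statistical Methods.
- Two-tailed level 0.05: an assumption. Statistical Methods gives no level, and 0.05 is the only one in the document.

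**Formula.** For n per group, the t statistic has 2n − 2 degrees of freedom and noncentrality d × √(n/2). Power is the probability that a noncentral t variable with these parameters exceeds the critical value (for the two-tailed test, in either direction).

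**Step 1: reproduce the plan's figures.** With n = 22 there are 42 degrees of freedom, and the noncentrality is 0.9 × √11 = 2.985. The one-tailed 0.05 critical value is 1.682, and power is **90.2%**. Solving for 90% power gives n = 21.86, which rounds up to 22. Dropout: 22 / 0.9 = 24.4, which rounds up to 25. All the stated figures reproduce, so the one-tailed calculation really was used and the word is not a slip.

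**Step 2: use the test that the trial runs.** With n = 22 and the same noncentrality, the two-tailed 0.05 critical value is 2.018, and power is **83.0%**.

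**Step 3: other sample sizes, d = 0.9, level 0.05**

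| n per group | Status | One-tailed power | Two-tailed power | Two-tailed chance of missing d = 0.9 |
|---|---|---|---|---|
| 22 | planned evaluable | 90.2% | 83.0% | 17.0% |
| 24 | analysed | 92.3% | 86.3% | 13.7% |
| 25 | recruited, no dropout | 93.2% | 87.7% | 12.3% |

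The two-tailed test does not reach 90% at any of these sizes.

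**Step 4: what 90% two-tailed would take.** The solution is n = 26.94, so 27 evaluable per group. With 10% dropout, 27 / 0.9 = 30 per group, or 60 in total. Put the other way, the effect detectable with 90% power two-tailed is d = 1.00 at 22 per group and d = 0.96 at 24 per group.

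**Step 5: where the two conventions disagree.** At 24 per group (46 degrees of freedom) the critical values are 1.68 one-tailed and 2.01 two-tailed. Dividing by √(24/2) = 3.464 gives observed standardised differences of 0.48 and 0.58. A difference in favour of FitMi Plus between these values is significant one-tailed and not significant two-tailed.

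**The case against.** The strongest reply has four parts.

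- **The realised shortfall is smaller.** Recruitment is complete and 24 per group were analysed, so a reader of the results faces 86.3% power. That is under 4 points below the stated 90%, and above the common 80% benchmark. This stands. The 83% describes the planned 22 per group, and both figures should be reported.
- **A sample-size assumption is not a decision rule.** Statistical Methods names only the two-tailed test, which is the more conservative choice, so the type I error is not inflated. This also stands. The p = 0.07 example applies only when the difference favours FitMi Plus, and it is a secondary argument. The main defect is the power figure.
- **The two-tailed level is not stated.** A two-tailed level of 0.10 would bring power at 22 per group back to about 90%. That is true, but the document nowhere gives such a level. If it was intended, it has to be written down, so a correction is needed either way.
- **Removing all mention of the one-tailed basis would hide how the trial was sized.** This is a fair point about the remedy, and the fix below allows for it.

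None of this removes the mismatch between the two sections.

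**Conclusion.** The concern holds. The arithmetic behind 22 per group is correct for a one-tailed test, but the primary analysis is two-tailed and the document does not reconcile the two. For the test the trial runs, the stated power is too high by about 7 points at the planned size (90% against 83.0%) and by just under 4 points at the analysed size (90% against 86.3%).

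This rests on carrying the 0.05 level over to the two-tailed test and on the plan's own d = 0.9, equal group sizes and unadjusted t-test. The validity of the primary test and of its estimate is not affected.

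**What to change.** Keep the two-tailed test as the single binding analysis of the primary outcome, and state its 0.05 level in Statistical Methods. Restate the sample-size paragraph for that test, and say openly that the trial was first sized with a one-tailed calculation, so that the record of how 22 was reached is kept. Suggested wording:

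> The sample size was originally derived for a one-tailed t-test at 0.05. The primary analysis is a two-tailed t-test at 0.05. With d = 0.9, this test has 83% power with 22 evaluable participants per group and 86% with the 24 per group analysed. It has 90% power for d of about 1.0 with 22 per group and about 0.96 with 24 per group.

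The one-tailed test should appear only as this historical note and not as a rule for declaring significance. The change is one of wording. It costs a less favourable power figure and needs no more participants and no new analysis.

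### Randomisation is stratified by FM level, but both change scores are compared with a t-test that ignores the strata: valid, but conservative and slightly wasteful

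*Combined protocol and SAP*

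**What the plan says.** The randomisation paragraph of the Participants section gives the purpose of the stratification: "Adaptive randomization was used to ensure matched levels of impairment between the FitMi Plus and FitMi Basic groups". It names one factor, baseline FM, cut into two levels ("subjects were stratified by their UE FM Score into two levels (i.e. 15-35, 36-55"), and says that participants were "and then randomized by alternating block allocation". Block size and the number of participants in each stratum are not given.

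Statistical Methods describes both analyses. The primary outcome, change in MAL from baseline to one-month follow-up, was "compared between FitMi Plus group and FitMi Basic group using an unpaired two-tailed t-test". For the secondary outcome, "change in Upper Extremity Fugl-Meyer Score from baseline to one-month post-therapy was compared between groups using an unpaired two-tailed t-test". The analysed sample is 48, with 24 per arm. No stratum term, baseline covariate or stratified test is described anywhere in the document, and the sample-size calculation also assumes a plain t-test.

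**The concern.** The analysis does not follow the design. When arms are balanced within FM levels, a difference in mean change between the two levels affects both arms almost equally and cancels from the treatment difference. The unpaired t-test takes its error variance from the full spread within each arm, which still contains that difference. The estimated standard error therefore exceeds the true one whenever FM level predicts change.

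The point estimate is not at risk, and neither is the protection against a false positive. What is at risk is sensitivity. The p-value tends to be too large, an interval built from the t-test is too wide, and with 24 per arm a real difference is somewhat more likely to be missed. The trial did the work of stratifying but collects only part of the precision it bought.

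**Working it through.** **Inputs from the documents.** Two FM strata; 24 analysed per arm; d = 0.9; an unpaired two-tailed t-test. The 0.05 level is the one given with the sample size.

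**Inputs assumed.** R², the share of within-arm variance in the change score explained by FM level, shown as a range. Two strata of 24, each split 12:12 between arms. Total within-arm variance is set to 1, so d is on the total SD.

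**The plan's own figure.** A one-tailed t-test at 0.05 with d = 0.9 and 22 per group has power 90.2%, and 22 / 0.9 = 24.4, which rounds up to 25. The stated 22 and 25 reproduce. For the two-tailed test actually described, 24 per arm gives 86.3%. That is the baseline below; the change from one tail to two is a separate matter and adds no weight here.

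**Standard error.** With exact 12:12 balance, the true variance of the arm difference is (1 − R²)(1/24 + 1/24) = (1 − R²)/12. The t-test's pooled variance has expectation (1 − R²) + R² × 48/46. The 48/46 arises because the between-stratum sum of squares within arms, 48R², is divided by 46 degrees of freedom. The correct standard error relative to the t-test's is therefore about

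√[(1 − R²) / (1 − R² + 48R²/46)].

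At R² = 0.10 this is √(0.90/1.00435) = 0.947. At R² = 0.20 it is √(0.80/1.0087) = 0.891.

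**Power with the stratum term.** Noncentral t on 45 df, with noncentrality 0.9 × √12 / √(1 − R²). At R² = 0.10 this is 3.118/0.9487 = 3.286, giving 89.5%. At R² = 0.20 it is 3.118/0.8944 = 3.486, giving 92.7%.

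**Simulation.** 200,000 trials per setting, with both analyses run on the same data, two-sided 5%:

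| R² | Error rate, t-test | Error rate, with stratum | Power, t-test | Power, with stratum | CI width ratio |
|---|---|---|---|---|---|
| 0 | 5.0% | 5.0% | 86.3% | 86.2% | 1.000 |
| 0.02 | 4.8% | 5.0% | 86.4% | 86.9% | 0.990 |
| 0.05 | 4.4% | 5.0% | 86.8% | 87.9% | 0.974 |
| 0.10 | 3.8% | 4.9% | 87.4% | 89.6% | 0.947 |
| 0.20 | 2.8% | 4.9% | 88.7% | 92.8% | 0.891 |
| 0.30 | 1.9% | 5.0% | 90.1% | 95.5% | 0.831 |

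The t-test's power also rises with R², so part of the benefit of stratifying is kept. The power figures with the stratum term agree with the noncentral t values within simulation error.

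**Is stratification the cause?** With simple 24:24 randomisation that ignores the strata, the t-test's error rate at R² = 0.30 is 5.1%. With blocks inside strata it is about 2.0%. The conservatism comes from ignoring the strata in the analysis.

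**Does it depend on exact balance?** No. With permuted blocks of 2 to 8, randomly filled strata, 50 enrolled and two lost at random, the t-test's error rate is 4.3–4.5%, 4.0–4.1% and 2.9–3.1% at R² = 0.05, 0.10 and 0.20, and the power gain is again about 1, 2 and 4 points. A 16/32 split of the strata gives nearly the same figures.

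**Smaller effects.** If the true effect were d = 0.6 (an assumption), power would be 52.8% against 57.1% at R² = 0.10, and about 53% against 62% at R² = 0.20. The gain is then about 4 and 9 points.

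**The case against.** The strongest reply is that the planned test is valid, and the larger gains need an FM effect for which the documents give no evidence. With two equal strata, R² = δ²/4, where δ is the difference in mean change between the strata in SD units, so δ = 2√R². R² of 0.02, 0.05, 0.10 and 0.20 requires strata that differ by 0.28, 0.45, 0.63 and 0.89 SD in mean *change*. The 4-point gain therefore needs a stratum effect about as large as the assumed treatment effect. Because both outcomes are change scores, it is not enough that FM level predicts the score itself. At R² = 0.05 and d = 0.9, the two analyses reach different significance verdicts in only about 1.3% of simulated trials. The sample size took no credit for stratification, so nothing promised has been lost. In any single trial the adjusted p-value can move either way.

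All of this is right, and it limits the size of the point. It does not remove it. FM is the one factor that the investigators chose to match on, and for the secondary outcome baseline FM is part of the change score itself, so some association is plausible. If there is none, the stratum term costs nothing visible.

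A second reply is that the trial is complete and a choice of models after the fact invites selection. That stands, and it is a reason to fix one form of the model and keep the t-test in view.

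**Conclusion.** The concern holds as a modest loss of efficiency. The unpaired t-test does not reflect the stratified allocation; it is conservative, not biased, and a significant result from it remains safe. For R² up to 0.10 the loss at d = 0.9 is about 0 to 2 power points, and a 95% interval would be up to about 5% wider than it need be measured by the ratio above (0.947). At R² = 0.20 the loss is about 4 points.

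These sizes rest on an assumed R² and on assumed stratum and block sizes, so the actual loss cannot be bounded away from zero. The direction does not depend on those assumptions: any scheme that balances the arms within FM levels gives it. The change is worth making because it brings the analysis into line with the design at almost no cost, but the trial's conclusions do not hinge on it.

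**What to change.** For MAL change and for FM change, fit a linear model with treatment and the FM stratum indicator (15–35 against 36–55). Report the adjusted treatment difference with its 95% CI and two-sided p-value. Use this one form for both outcomes; the figures above apply to the indicator and were not computed for continuous baseline FM.

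Because Statistical Methods already reports the final sample of 48, keep the stated unpaired t-test, show the adjusted result beside it, and say that the model was added after the sample was known. A site term is optional and is not part of this point.

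The cost is one extra model per outcome, using a variable already recorded at baseline, and one degree of freedom (45 instead of 46).

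### Change in MAL and in FM is tested without baseline adjustment, although both baselines are in hand: a likely loss of precision, not an error

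*Combined protocol and SAP*

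**What the plan says.** Statistical Methods gives the primary analysis in one sentence: change in MAL from baseline to one month "was compared between FitMi Plus group and FitMi Basic group using an unpaired two-tailed t-test". The secondary analysis has the same form: "change in Upper Extremity Fugl-Meyer Score from baseline to one-month post-therapy was compared between groups using an unpaired two-tailed t-test". No section mentions a covariate, ANCOVA, or adjustment for the randomisation stratum or for site.

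Both baselines exist. Outcomes states that "MAL was assessed at baseline and one-month follow-up" and defines the secondary measure as "change in Upper Extremity Fugl-Meyer (FM) Score from baseline to one-month post-therapy". Trial Design adds: "Participants were invited for an initial assessment to confirm they met the inclusion criteria and to establish baseline measures". FM also determines eligibility and defines the randomisation strata: "subjects were stratified by their UE FM Score into two levels", namely 15-35 and 36-55 (Participants).

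The effect size is Cohen's d = 0.9, "based on long-term follow-up data from a previous study (N=18) of functionally oriented home-based exercise with MusicGlove" (Participants). The scale on which it is standardised (change or raw score) is not stated. The analysed sample is 24 per arm: "Two participant did not return for long term follow-up and were excluded from final analysis, leading to a final n=48".

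**The concern.** A change score subtracts the whole baseline value, which fixes the baseline coefficient at 1. If the slope of follow-up on baseline is below 1, as regression to the mean usually makes it, subtraction over-corrects and leaves removable noise in the comparison. ANCOVA estimates the slope instead.

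Two things are at stake. The first is precision: the sample is fixed at 24 per arm, so baseline data already held are the cheapest route to a narrower interval. The second is chance imbalance: an unadjusted change contrast moves with any baseline difference between arms. That point bears mainly on MAL, which is not a stratification factor and is balanced only as far as it correlates with FM. For FM, stratification already limits imbalance.

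**Working it through.** **Inputs from the documents.** d = 0.9; planned n = 22 per group at 90% power, one-tailed 0.05; 10% dropout; analysed n = 24 per arm; two-tailed t-test on change.

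**Inputs assumed.** r, the baseline to follow-up correlation, over 0.5 to 0.95; k, the ratio of follow-up SD to baseline SD, at 1 and then varied; d = 0.9 on the change scale; two-tailed alpha 0.05. The documents give none of r, k or the scale of d.

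**1. The plan's own figure.** n = 2(1.645 + 1.282)² / 0.9² = 21.2, rounded up to 22. Noncentral-t power at 22 per group, one-tailed, is 90.2%. Then 22 / 0.90 = 24.4, rounded up to 25. The stated figures reproduce.

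**2. Power of the stated analysis.** At 24 per arm the noncentrality is 0.9 / √(2/24) = 3.118 on 46 df, giving two-tailed power of 86.3%. (The one-tailed sizing against a two-tailed analysis is a separate issue.)

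**3. Relative variance of ANCOVA.** In units of baseline variance, change has variance 1 + k² − 2rk, and the ANCOVA residual has k²(1 − r²). Estimating the slope at N = 48 costs a factor of about 1 + 1/(48 − 4) = 45/44. So

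R = k²(1 − r²) / (1 + k² − 2rk) × 45/44,

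which at k = 1 is (1 + r)/2 × 45/44. ANCOVA power uses an effect of 0.9/√R on 45 df.

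| r (k = 1) | R | Equivalent extra participants (1/R − 1) | ANCOVA power |
|---|---|---|---|
| 0.5 | 0.767 | 30% | 93.6% |
| 0.7 | 0.869 | 15% | 90.5% |
| 0.8 | 0.920 | 9% | 88.9% |
| 0.9 | 0.972 | 3% | 87.2% |
| 0.95 | 0.997 | 0.3% | 86.3% |

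Break-even in variance is at r = 2 × 44/45 − 1 = 0.956. Power of 90% is reached only for r up to 0.73. The largest expected loss, when the slope rk equals 1, is R = 45/44: 2.3% of variance, with power 85.5%.

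**4. Unequal SDs.**
- k = 1.25: power is 85.5% to 86.1% for r = 0.7 to 0.85, so no gain.
- k = 1.1: power is 88.2%, 86.6%, 85.9%, 85.5% and 86.0% at r = 0.7, 0.8, 0.85, 0.9 and 0.95.
- k = 0.8: power is at least 96.8% at r = 0.5, 0.7, 0.9 and 0.95.

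**5. Simulation check.** 20,000 runs per setting, k = 1, FM strata cut at the median (assumed), arms balanced within stratum.
- MAL unrelated to FM, t-test against ANCOVA power: 86.1% v 93.6% (r = 0.5), 86.4% v 90.7% (0.7), 86.3% v 87.2% (0.9), 86.4% v 86.3% (0.95).
- FM: 88.1% v 93.9%, 87.7% v 91.3% and 86.6% v 87.7% at r = 0.5, 0.7 and 0.9.
- FM type I error, t-test against ANCOVA: 0.031 v 0.049, 0.041 v 0.049 and 0.048 v 0.052 at the same r. The FM t-test is valid but somewhat conservative, because its standard error ignores the stratification.

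**6. Chance imbalance.** With a median split, the variance of a baseline variable that correlates c with FM falls within strata to 1 − c² × 2/π. The SD of the arm difference is √{(2/24)(1 − 2c²/π)}: 0.289, 0.265 and 0.239 for c = 0, 0.5 and 0.7. A MAL imbalance above 0.3 SD then occurs in about 30%, 26% and 21% of trials. For FM itself (c = 1) the SD is 0.174 and the chance about 8.5%; the simulation gave 0.18 and about 10%.

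At k = 1, a 0.3 SD imbalance shifts the change contrast by 0.3(1 − r)/√{2(1 − r)} = 0.15, 0.12, 0.07 and 0.05 SD of change at r = 0.5, 0.7, 0.9 and 0.95, in either direction.

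**The case against.** The strongest reply is that nothing here is wrong. Both outcomes are defined as change, the trial was sized for a t-test, and a t-test on change was used. ANCOVA is a choice between two valid methods. That stands, and is why the point is a recommendation and not an error.

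Second, Statistical Methods is in the past tense and the document is dated 12/31/2023. If the blind is already broken, an adjusted model cannot replace the primary test, so the power gain cannot reach it. That also stands. What remains is a supplementary estimate, usually with a narrower interval.

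Third, the size of the gain is uncertain. It largely disappears at high r, or if follow-up scores are only slightly more variable than baseline scores (k = 1.1, r of 0.8 or more). For FM, eligibility truncates baseline to 15-55 but not follow-up, so k above 1 is plausible there. If d = 0.9 was standardised on the raw SD, t-test against ANCOVA power at k = 1 is 86.3% v 93.6% at r = 0.5, 97.6% v 98.8% at 0.7 and 99.8% v 99.9% at 0.8. From r = 0.7 the power gain is then about a point or less, although the variance ratio R and the gain in interval width are unchanged. All of this limits the size of the benefit. It does not reverse the trade: the expected downside is capped at 0.8 points of power.

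Fourth, no baseline imbalance is reported, so the imbalance argument describes a possible shift. That is correct; the shift is also modest beside an assumed effect of 0.9.

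**Conclusion.** The concern holds as an efficiency point. The change-score t-tests are valid, but they leave collected baseline information unused. With equal SDs and d on the change scale, adjustment raises two-tailed power from 86.3% to between 87.2% (r = 0.9) and 93.6% (r = 0.5), the equivalent of about 3% to 30% more participants. The gain is nil near r = 0.95, or wherever the slope of follow-up on baseline approaches 1; the worst expected cost is 2.3% of variance. The power gain for FM is similar to that for MAL; only the protection against chance imbalance is mainly a MAL matter. The principle is secure. Its size in this trial rests on r and k, which the documents do not give and the sponsor can compute from its own data. Grade: should be done, not must.

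**What to change.** Fit a linear model of one-month MAL (or, equivalently for the group effect, MAL change) on group and baseline MAL, and the same for FM with baseline FM. Report the adjusted difference with a 95% CI, together with the observed r and the baseline and follow-up SDs so that readers can judge the gain. Adding the FM stratum or baseline FM to the MAL model is an optional extension that would reflect the randomisation.

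Make the adjusted model primary only if it is specified before unblinding. Otherwise keep the t-test as the primary result and show the adjusted estimate beside it, labelled post hoc.

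The cost is one degree of freedom per covariate and no new data.

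### Does leaving two of the 50 participants out of the final comparison, with no sensitivity analysis, undermine the result?

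*Combined protocol and SAP*

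**What the plan says.** The Statistical Methods section gives the participant flow: "We recruited 50 total participants across both study sites", then "Two participant did not return for long term follow-up and were excluded from final analysis", which leaves 48, "with 24 participants in the FitMi Plus group and 24 participants in the FitMi Basic group". Change in Motor Activity Log (MAL) from baseline to one month "was compared between FitMi Plus group and FitMi Basic group using an unpaired two-tailed t-test". The Fugl-Meyer (FM) comparison follows without its own sample size: "Similarly, change in Upper Extremity Fugl-Meyer Score from baseline to one-month post-therapy was compared between groups". The natural reading is that the same 48 are used for both.

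The sample-size paragraph under Participants asks for 22 per group and adds a margin for loss: "To account for 10% dropout, we will recruit 25 participants in each group". Outcomes gives the timing of the primary measure: "MAL was assessed at baseline and one-month follow-up".

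The document describes no imputation, best- or worst-case bound, or tipping-point analysis. It also does not say which arm each of the two came from or why they did not return.

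**The concern.** Comparing only those who came back can bias a randomised comparison if the reason for not returning is related to outcome and differs between arms. A 10% recruitment margin protects power. It says nothing about bias. In a trial of 50, each person is about 4% of an arm, so two unusual values can move a borderline p-value across 0.05. MAL has no value between baseline and one month that could help to predict the missing ones. With no sensitivity analysis, a reader cannot see how far the conclusion depends on two people. At stake would be the primary MAL conclusion and, on the natural reading, the FM conclusion too.

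**Working it through.** **Inputs.** Under Participants: d = 0.9, one-tailed 0.05, 90% power, 22 per group, 10% loss, 25 per group. Under Statistical Methods: 50 recruited, 2 lost, 24 v 24 analysed, two-tailed t-test. Assumed, because the documents report no results: SD of change equal to 1 in each arm, one loss per arm, and various p-values on the 48.

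**1. The plan's own figures.**
- Sample size by normal approximation: 2(1.645 + 1.282)²/0.9² = 21.15, which rounds up to 22 per group. Exact one-tailed t-test power at 22 per group is 90.2%.
- Margin for loss: 22/0.9 = 24.4, which rounds up to 25.
- Flow: 50 − 2 = 48 = 24 + 24.
- Loss: 2/50 = 4.0%.

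All of these reproduce.

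**2. Cost in power.** At d = 0.9, going from 25 to 24 per arm lowers one-tailed power from 93.2% to 92.3%, and two-tailed power from 87.7% to 86.3%. The loss of two participants costs about one point. The one-tailed sample size beside a two-tailed analysis is a separate matter and does not bear on this one.

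**3. How far two missing values can move the result.** Draw each missing change from its own arm's distribution. Shift it by k SD, in opposite directions in the two arms, and combine over many imputations by Rubin's rules.
- Difference: D ∓ 2k/25 = D ∓ 0.08k, where D is the difference in the 48.
- Variance: 2(1 + 0.04k²)/25 within imputations, plus 2/600 between imputations.
- Degrees of freedom (Barnard–Rubin): about 44.

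Start exactly at the threshold: p = 0.050, t = 2.013 on 46 df, D = 2.013 × √(2/24) = 0.581.
- k = 0: variance 0.0800 + 0.0033 = 0.0833 = 2/24, so p stays at 0.050. This confirms that the method creates no false precision.
- k = 1: variance 0.0832 + 0.0033 = 0.0865, SE 0.294. Adverse: t = 0.501/0.294 = 1.703, p = 0.095. Favourable: t = 0.661/0.294 = 2.247, p = 0.030.
- k = 2: variance 0.0928 + 0.0033 = 0.0961, SE 0.310. Adverse: t = 0.421/0.310 = 1.358, p = 0.181. Favourable: t = 0.741/0.310 = 2.390, p = 0.021.
- Both shifted the same way: D is unchanged, and p is 0.054 at 1 SD and 0.067 at 2 SD.

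**4. Adverse shift needed in both participants to lose significance.**

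| p on the 48 | Shift needed (SD) |
|---|---|
| 0.04 | 0.34 |
| 0.03 | 0.74 |
| 0.02 | 1.22 |
| 0.01 | 1.93 |
| 0.003 (d = 0.9, t = 3.118) | 2.89 |

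Counting crossings in either direction, only p-values of about 0.024 to 0.082 on the 48 could cross 0.05 with 1 SD shifts, and about 0.009 to 0.114 with 2 SD shifts. If both losses came from one arm, the threshold example is almost the same: 0.031 to 0.094 at 1 SD and 0.022 to 0.175 at 2 SD.

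**The case for a change.** The strongest case for the concern is that 4% missing is not automatically harmless in a trial this small. At p = 0.03, an adverse shift of 0.74 SD in two people is not extreme, and it would reverse the conclusion. The data are already held, the extra analysis is slight work, and it would help the sponsor if the result lies far from 0.05.

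Much of that stands as arithmetic. The document does leave open which arm each loss came from and why, and a reader would be glad to have both.

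It does not show a fault in the plan. The vulnerable range is reached only by assuming a p-value the documents do not give. The larger movements also need both people to depart in opposite directions, each against the observed difference. Departures in the same direction barely move p. Nor is an assumed shift the only possible check. Baseline MAL, and the FM score used for eligibility and stratification, should exist for both participants and could support a missing-at-random analysis. A shift is needed only to probe departures from that. Any such analysis would leave the 48-participant t-test as the main result.

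**Conclusion.** The concern does not hold. The flow figures agree, the 4% loss is inside the 10% margin, 24 per arm exceeds the 22 required, and all participants with one-month data appear to be in the comparison. Nothing in the documents points to bias. At the only effect size they state (d = 0.9), about 2.9 SD of adverse departure in both missing participants would be needed to change the conclusion. A result close to 0.05 would be more fragile, but no such result is reported. A sensitivity analysis here is a reviewer's preference for thoroughness, and leaving it out does not make the estimate, test or decision rule wrong.

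This rests on four readings or assumptions: the two had been randomised (the Trial Design section gives the randomised trial as N=50, and 25 per group were planned); the same exclusion covers FM; one loss fell in each arm, which fits the 24/24 split but is not stated, and matters little to the figures; and the SDs of the two arms are equal.
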